# 13.5. Confidentiality of Subject's PGx Data

GSK advises that participation in this PGx research, withdrawal from this research, sample destruction, and/or PGx results should not be documented in the subject's medical records. Storage of information regarding the PGx research with source documents for the study is permissible if stored in the investigator study files.

Coded PGx samples and results will be associated with the subject's study specific number in computer databases. Coded PGx research results may be submitted to regulatory agencies as part of an investigational product submission and/or included in a research publication.

Individual genotype results will only be shared with a subject through the investigator if the subject requests to see their results. The results are for research purposes only, the clinically significance of which could be undetermined as such an early stage of research and not immediately useful to the subject's health. GSK will not release individual PGx results to anyone else (e.g., family members, primary care physicians, insurers, or employers) under any circumstance, unless required by law.

# 13.6. Subject Withdrawal

If a subject who has consented to participate in PGx research withdraws from the clinical study for any reason other than lost to follow-up, the subject will be given the following options concerning the PGx sample if already collected:

- PGx research continues per the subject's consent; or
- Any remaining sample is destroyed.

If a subject withdraws consent from the PGx research or requests sample destruction, the investigator must complete the appropriate documentation to request sample destruction within the timeframe specified by GSK and maintain the documentation in the site study records. In either case, GSK will only keep and study information collected/generated up to that point.

# 13.7. PGx Data Management

Data from the case report forms and PGx research using the coded sample will be stored electronically. International regulations for information on computers and relevant laws on processing personal information will be followed.

# 13.8. Pharmacogenetics Analyses

If at any time it appears that there is a potential unexpected or unexplained variation in drug handling or response (e.g., pharmacokinetics, efficacy and/or safety) that may be attributable to genetic variation, then PGx analysis may be conducted. In these circumstances the analysis undertaken will be limited to PGx analysis of response to or handling of GW572016.

Generally GSK will utilize two approaches to explore genetic variation in drug handling or response.

- Hypothesis driven approach: A specific hypothesis is generated about sections of DNA (or individual single nucleotide polymorphisms (SNPs) or other genetic markers) that may be associated with differential drug handling or response. Specific sections of DNA may be selected from areas of the genome (e.g., candidate genes) known to encode the drug target, drug metabolizing enzymes, areas associated with mechanisms underlying adverse events, and those linked to study disease and, thus, linked to drug response.
- 2. Genome-wide approach utilizing polymorphic markers (e.g., SNPs): By evaluating large numbers of polymorphic markers throughout the genome, sets of markers may be identified that correspond to differential drug response or handling.

Analysis of genetic markers (e.g., whether within candidate genes or SNPs studied in a genome-wide analysis) will include the following considerations. The genotypic frequencies of each polymorphism will be evaluated for conformity to those expected under normal conditions by employing Hardy-Weinberg Equilibrium testing. Any departure from expectation will be taken into account, possibly signaling a data error or alternatively a connection between the polymorphism and breast cancer.

For pairs of polymorphisms, the degree to which alleles from the two sites are correlated (linkage disequilibrium) may also be evaluated. If the genotypes at two polymorphic sites within a gene are shown to be statistically associated with a response to investigational product, the degree of linkage disequilibrium will aid interpretation in that it will indicate the extent to which the two sites are exerting independent effects.

A decision regarding the construction and analysis of marker haplotypes -- combinations of alleles from different polymorphic sites that are inherited from one parent -- may be guided by the assessment of linkage disequilibrium. For example, if there is no linkage disequilibrium between polymorphic sites, then haplotype construction will be uninformative.

Differences in baseline clinical characteristics and potential contributing covariates may be summarized and compared among genotype (or haplotype) subgroups.

Analyses may be carried out to evaluate the degree of association between subject genotype (or haplotype) and selected parameters (e.g., efficacy and safety). Where such genotypic tests are inappropriate (for example, where the number of marker genotypes is too large and/or the frequency of individual genotypes too small), allelic tests may be conducted. Allelic tests evaluate whether the frequency of each marker allele is the same in responders and non-responders.

In addition to evaluating the main effects of the genotypes (haplotypes or alleles) on the selected parameters, the possibility of a treatment group by genotype (haplotype or allele) interaction may also be explored. If appropriate, the joint effects of multiple markers (gene-gene interactions) may also be evaluated.

#### **Sample Size Considerations**

The ability to detect differential drug response or handling among genotypes at a polymorphic site depends on the total number of subjects genotyped and the frequency distribution of the different genotypes. Consequently, genotyping analyses are plausible for those polymorphic sites where the number of subjects comprising the genotypic groups is sufficiently large; however, these frequencies will not be known until sufficient samples have been collected and genotyping is complete.

Estimates of sample sizes required to demonstrate genotype effects vary considerably, depending on the assumptions made about allele frequency, genetic effect size, and mechanism of inheritance [Cardon, 2000]. In the work by Palmer and Cookson [Palmer, 2001], which assumed a genotype relative risk of 1.5, it was estimated that more than 300 cases and 600 controls would be needed to conduct a genetic association analysis. In contrast, McCarthy and Hilfiker [McCarthy, 2000] showed that with a

genotype relative risk of 2.16 and a relatively commonly occurring genotype, only 30 cases and 30 controls would be needed to demonstrate an association. Consequently, it is quite possible that effects with relatively large genotype relative risks may be detectable in individual Phase I or Phase II studies. A range of examples exist to demonstrate robust and clinically relevant PGx data may be generated from PGx studies with sample sizes far less than the sizes proposed by Palmer and Cookson.

Published PGx examples include abacavir hypersensitivity reaction [Hetherington, 2002; Mallal, 2002] and tranilast induced hyperbilirubinemia [Roses, 2002] where genetic markers have been found to significantly associate with hypersensitivity reaction (abacavir) and hyperbilirubinemia (tranilast). These examples show that small sample sizes typically encountered in Phase I and Phase II studies may be sufficient to identify clinically relevant genetic associations.

## 15. **APPENDICES**

## 15.1. Appendix 1: ECOG Performance Status Scale

Grade	ECOG
0	Fully active, able to carry on all pre-disease performance without restriction
1	Restricted in physically strenuous activity, but ambulatory and able to carry out work of a light or sedentary nature, e.g., light house work, office work
2	Ambulatory and capable of all selfcare, but unable to carry out any work activities. Up and about more than 50% of waking hours
3	Capable of only limited selfcare, confined to bed or chair more than 50% of waking hours
4	Completely disabled. Cannot carry on any selfcare. Totally confined to bed or chair
5	Dead

Abbreviations: ECOG = Eastern Cooperative Oncology Group

# **15.2.** Appendix 2: Cockcroft and Gault Method for Calculated Creatinine Clearance

Creatinine clearance can be calculated from serum creatinine values by one of the two formulas below:

Calculated creatinine	(140 – age [yrs]) × weight (kg)
clearance (mL/min) =	$72 \times \text{serum creatinine (mg/DL)}$
Female patients: multiply by 0.85	

In order to use SI units for creatinine ( $\mu$ mol/L), the following formula may be used.

Calculated creatinine
clearance (mL/min) = $(140 - age [yrs]) \times weight (kg) \times 1.23$ 
serum creatinine (µmol/L))Female patients: multiply by 0.85

### 15.3. Appendix 3: MATERIAL and METHOD

# 1. Preparation of blood sample and isolation and enumeration of CTCs in advanced breast cancer patients.

Immunicon is developing and commercializing diagnostic and research products for tumour cell analysis. Reagent kits incorporating Immunicon proprietary technology are used to capture, count and characterize circulating tumour cells or circulating endothelial cells from whole blood.

The CellTracks AutoPrep System is an automated sample preparation system for immunomagnetic cell selection. Reagents are added to each specimen and magnetic incubations are precisely timed. Many steps are automated, minimizing user interaction. Depending on the processing protocol, samples may be analyzed using the CellTracks Analyzer II (a semi-automated fluorescence microscope used to count and characterize the cells isolated by the CellTracks AutoPrep System.), flow cytometry or processed offline for molecular analysis.

#### Analysis of Circulating Tumour Cells (CTCs)

The CellSearch Circulating Tumour Cell Kit is intended for the enumeration of circulating tumour cells (CTC) of epithelial origin (CD45-, EpCAM+, and cytokeratins 8, 18+, and/or 19+) in whole blood.

The presence of CTC in the peripheral blood, as detected by the CellSearch Circulating Tumour Cell Kit, is associated with decreased progression free survival and decreased overall survival in patients treated for metastatic breast cancer. A CTC count of 5 or more per 7.5 mL of blood is predictive of shorter progression free survival and overall survival in metastatic breast cancer patients (Cristofanilli et al).

Products and method for Analysis of Circulating Tumour Cells (CTCs):

- CellSave Preservative Tubes, intended for the collection and preservation of circulating epithelial cells (tumour cells) in whole blood, to be used for enumeration and phenotyping. Samples are stable for 72 hours after collection.
- CellTracks AutoPrep System
- CellTracks Analyzer II
- CellSearch EGFr Tumour Phenotyping Reagent: a fluorescein conjugated monoclonal antibody anti -EGFr designed to be processed on the CellTracks AutoPrep System with the CellSearch Circulating Tumour Cell Kit and analyzed with the CellTracks Analyzer II.

- CellSearch Circulating Tumour Cell Kit (Veridex). The kit contains reagents and supplies for 16 tests (14 patients samples + 2 control samples) including:
  - Anti-EpCAM Ferrofluid: to capture epithelial cells
  - Nucleic Acid Dye: DAPI to identify nucleated cells
  - Capture Enhancement Reagent: to maximize capture efficiency regardless of variable EpCAM expression
  - Permeabilization Reagent
  - Cell Fixative: to fix cells in the final samples
  - Staining Reagent: Anti-cytokeratin-PE and anti-CD45-APC to label epithelial cells and leukocytes respectively. A 4th color may be added to further characterize the cells (markers for HER2, EGFr or MUC-1 analysis)
  - CellTracks AutoPrep sample tubes, caps and cartridges

This technology enables essentially all of the cells from the starting samples (7.5 ml) to be analyzed with minimal loss.

10 ml of patient's blood is collected into CellSave Preservative Tubes (Immunicon) to ensure that cell morphology and antigen expression are preserved. Fill tube must be gently invert 8 times to prevent clotting and store at room temperature (15-30°C) until processing.

Samples will be stable for up to 72 hours and must be processed within 72 hours of collection.

Each sample must be examined for clotting before processing on CellTracks AutoPrep System. Clotted samples should be discarded because clots interfere with the performance of the assay.

**7.5 ml** blood from CellSave Preservative Tubes (Immunicon) is transfed into the conical AutoPrep tube (Immunicon) and 6.5 ml Dilution Buffer is added. Sample is mixed by inversion 5 times and then centrifuged at 800xg for 10 minutes with brake off.

The sample must be processed on the CellTracks Autoprep System within 1 hour of sample preparation.

The conical AutoPrep tube (Immunicon) and reagent kit (CellSearch Circulating Tumour Cell Kit) are loaded on CellTracks AutoPrep System (Immunicon). The CellTracks AutoPrep System automates and standardizes complex sample preparation operations.(Ferrofluid and staining reagents are added to each specimen, magnetic incubations are precisely timed and the final, enriched sample is dispensed into the MagNest cell presentation device).

#### GM2007/00215/03

#### CONFIDENTIAL

Ferrofluids conjugated to antibodies directed against EpCam protein are used for isolation of CTCs from 7.5 ml whole blood. After the cells are enriched from the patient sample and fluorescently labelled with staining reagent and nucleic acid dye. The CellSearch HER2 Tumour Phenotyping Reagent is added to identify those CTCs over-expressing HER2.

Magnetic incubations are precisely timed and the final enriched sample is dispensed into the MagNest(Immunicon) cell presentation device that exerts a magnetic field that causes the magnetically labeled cells to form a monolayer on one focal plane inside the reaction cartridge. The filled cartridge within the MagNest device should be allowed to incubate in the dark for minimum of 20 minutes and analyzed within 24 hours.

The CellTracks Analyzer II (Immunicon) scans the reaction cartridge and displays a gallery of images of candidate targets to the user for classification. Captured images containing PE and DAPI positive events are presented in a gallery for analysis and classification of cells by the user, so cells CK+/DAPI+/CD45 are classified as CTCs and an event is classified as a tumour cell expressing HER-2 when its morphological features are consistent with that of a tumour cell and it exhibits the phenotype EpCAM +/CK+/DAPI+/CD45- and HER2 + .

The CellSearch Circulating Tumour Cell Control Kit (Veridex) is used to check reagents, instruments and operator technique. Each single use bottle contains two populations of a cultured cell line at different concentrations (Low and High). The two cell populations are differentially stained with fluorescent dyes that are specific for each population to permit simultaneous enumeration of Low and high Controls in one assay.

#### 2. Isolation of Circulating Tumour Cells (CTCs) by CellSearch Profile Kit

The presence of epithelial cells in peripheral blood in normal healthy patients is very rare, but they have been found in low number in several malignant disease.

The CellSearch Profile Kit (Veridex) is designed to immunomagnetically enrich cells of epithelial origin in whole blood in conjunction with the Celltracks AutoPrep system. When CTCs have been enriched from whole blood, researchers may wish to investigate RNA expression or genomic DNA in these cells. Recently, the ability to perform multigene RT-PCR profiling of CTCs as been demonstrated. Molecular profiling of CTCs should lead to improved characterization of CTCs and ultimately to develop of novel therapeutic strategies.

The CellSearch Profile Kit (Veridex) contains a ferrofluid-based capture reagent coated with antibodies targeting the Epithelial Cell Adhesion molecule (EpCAM) antigen for capturing CTC. The CellTrack AutoPrep System precisely dispenses reagents and performs magnetic incubation steps. The majority of leukocytes and other blood components are depleted from the final sample, rendering it ready for further analysis using the laboratory's validated methods and minimizing background.

#### GM2007/00215/03

#### CONFIDENTIAL

Products and method for isolation of Circulating Tumour Cells (CTCs):

- CellSave Preservative Tubes (cellular analysis) or EDTA tubes (molecular analysis) for blood collection
- CellTracks AutoPrep System
- CellSearch Profile Kit The kit contains reagents and supplies for 16 tests including:
  - Anti-EpCAM Ferrofluid: to capture epithelial cells
  - Capture Enhancement Reagent: to maximize capture efficiency regardless of variable EpCAM expression
  - Dilution Buffer
  - CellTracks AutoPrep sample tubes and caps

10 ml (at least 7.5 ml) of patient's blood is collected aseptically by venipuncture or from a venous port.

**For cellular analysis** of the epithelial cells must be used the CellSave Preservative Tubes because CTCs are fragile and require preservation for accurate analysis. Fill tube must be gently invert 8 times to prevent clotting and store at room temperature (15-30°C) until processing.

Samples will be stable for up to 72 hours and must be processed within 72 hours of collection.

Each sample must be examined for clotting before processing on CellTracks AutoPrep System. Clotted samples should be discarded because clots interfere with the performance of the assay.

**7.5 ml** blood from CellSave Preservative Tubes (Immunicon) or EDTA tubes is transfed into the conical AutoPrep tube (Immunicon) and 6.5 ml Dilution Buffer is added. Sample is mixed by inversion 5 times and then centrifuged at 800xg for 10 minutes with brake off.

The sample must be processed on the CellTracks Autoprep System within 1 hour of sample preparation. The CellTracks AutoPrep System delivers a final volume of 900 mcl of CTC enriched sample. The final sample is ready for further analysis using the laboratory's validated methods.

# 3. Assessment of HER2 status by FISH method on primary breast cancer tissue and on CTCs

FISH on primary tumour or metastatic slides and on CTCs will be performed using the PathVysion HER-2 DNA FISH Kit, (Vysis Inc, Downers Grove, IL) according to the manufacturer's instructions.

The PathVysion HER-2 DNA Probe Kit (PathVysion Kit) is designed to detect amplification of the HER-2/neu gene via fluorescence *in situ* hybridization (FISH) in formalin-fixed, paraffin-embedded human breast cancer tissue specimens

The kit incorporates two directly labelled fluorescence DNA probes: an orange probe directed against the *HER2* gene (HER2, 17q11.2-q12) and a green probe directed against the pericentromeric region of chromosome 17, (CEP 17, 17p11.1-q11.1), the chromosome in which the *HER2* gene resides. To breakdown formaldehyde cross-links, acid pretreatment and protease digestion were performed (Vysis paraffin pre-treatment kit; Vysis Inc), followed by standard saline citrate (SSC) and formamide denaturation (72°C, 5 minutes). After dehydration, the HER2/CEP 17 probe cocktail was added, and coverslips were applied and sealed with rubber cement. Slides were incubated in a humidity chamber overnight for 18 hours at 37°C. On the following day, slides were washed in a stringency buffer (SSC, NP40), air-dried in the dark and incubated with 4,6 diamidino-2- phenylindole (DAPI) for nuclear identification. Slides were stored in the dark, at 20°C.

The pathologist counts HER-2 gene copy numbers in interphase nuclei of malignant cells. Since the "natural biological standard" for normal cells dictates that they contain two copies of HER-2 gene, interpretation of HER-2 status using PathVysion FISH can be measured precisely and with objectivity. The cut-off between normal and abnormal is set by biology; more than one copy of the HER-2 gene per chromosome 17 is abnormal. Determination of the ratio of HER-2 to chromosome 17 copy number is useful in the discrimination of aneusomy of chromosome 17 from true HER-2 gene amplification. This allows for the proper assessment of amplification levels, especially low level amplification

### 15.4. Appendix 4: PET Scan Sub-Study

All patients who satisfy the protocol and additional eligibility criteria will be invited to enrol for this sub-study looking at the early effects of lapatinib on tumour proliferation and MAP kinase activity. All PET scans will be performed at HAMMERSMITH IMANET at Hammersmith Hospital, [name] by one of the principal investigators. All patients will be consented separately for the PET procedure.

**Title**: Imaging modulation of MAPkinase activity using [C]choline and [F]FLT PET.

**Background**. Growth receptor activation of EGFR and HER-2 receptors is responsible for reactivation of ERlpha transcription through various signal transduction pathways following endocrine therapy. This leads to relapse of breast tumours associated with aggressive progression and poor outcomes [Nicholson, 2003]. Downstream signalling from these receptors is mainly by the MAPkinase cascade and the PI3kinase pathway. The MAPkinase cascade activation results in ERK1/2 phosphorylation which in turn causes ER phosphorylation at Ser-118 position leading to its ligand-independent phosphorylation [Gee, 2001].

**Rationale**: There is an unmet need to quantify early response of new investigational agents as well as finding biomarkers of response to newer therapies like lapatinib. The use of PET would lead to a rapid way of testing the effectiveness of new therapies. We plan to quantify the early effects of lapatinib reflected in modulating MAPkinase activity using the radioactive PET tracer [C]choline and proliferation of tumour using [F]Fluorothymidine(FLT). Previous work by our group has shown that inhibition of MAP kinase(ERK1/2) results in a dose dependent and time dependent inhibition of phosphocholine production in-vitro [Liu, 2002]. [F]Fluorothymidine(FLT) is a tracer which measures proliferation by imaging in-vivo Thymidine Kinase-1 activity which is the enzyme responsible for phosphorylation of thymidine before its incorporation into DNA. [F]FLT is phosphorylated by thymidine kinase-1(TK1). This leads to intracellular trapping of the tracer and prevents its further incorporation into DNA. Thus this tracer provides a readout of proliferative activity as shown previously in our group [Kenny, 2005].

**Methods**: This PET substudy is planned to recruit up to 14 patients (using the same sample size calculation as in our previous study with similar tracers) who have diagnosed metastatic breast cancer or metastatic disease which is progressing in spite of treatment. All patients would need to be ER positive. The other receptor status will be as per the main study. Patients should also have received some form of adjuvant endocrine treatment in the past for breast cancer. All patients will undergo a pre-treatment single session PET scan using [C]choline and [F]FLT. Three 10mls venous blood samples would be taken during each PET scan (totalling 30mls per PET scan) to calculate radioactivity counts and metabolite of the [11C] choline radiotracer. They will then be asked to start 1500mg/day of oral lapatinib. At the end of approximately two weeks of treatment, the same PET scan will be repeated to find out if early change in uptake of both tracers is demonstrable, reflecting early activity of lapatinib.

**Statistical considerations**: From reproducibility studies using [18F]FLT in untreated and metastatic breast cancer conducted by the same team the calculated standard deviation (SD) for Ki (constant for net irreversible uptake of [18F]FLT) was 2.0 and 3.61 in untreated and metastatic patients and the mean was 3.6 and 7.3 respectively. Preliminary results for [11C]choline are not available but are expected to be similar.

A sample size of approximately 14 in each group will have 80% power to detect a difference in means of 3.7 (the difference between the metastatic group mean, m1, of 7.3 and the primary group mean, m2, of 3.6) assuming that the metastatic group standard deviation, s1, is 3.61 and the primary group standard deviation, s2, is 2 (ratio of primary group to metastatic group standard deviation is 0.554) using a Wilcoxon (Mann-Whitney) rank-sum test with a 0.05 two-sided significance level. Statistics power calculation done by [name], Imperial College Statistics Service.

**Results**: Dynamic images of PET will be analysed by drawing ROI (region of interest) around the tumours. A population arterial input function will be applied to the image data to derive various parameters of tracer delivery (K1) and irreversible uptake (Ki). Other parameters of uptake obtained will be SUV (standardised uptake value) and AUC (Area under tracer concentration-time curve). A significant change in uptake parameters from pre to post-treatment would imply inhibition of MAP kinase activity and proliferation due to the effect of lapatinib.

**Primary End Point**: Change in uptake of of [11C]choline and [18F]FLT from pre to post treatment with lapatinib.

The ability to image MAP kinase modulation using PET would serve as a marker of the pharmacological early effect of lapatinib.

Secondary End Point: None.

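### The PET sub-study's 80% power claim is for a two-group comparison of metastatic with primary tumours, not for its own one-group pre/post endpoint

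*Protocol*

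**What the plan says.** All of this is in Protocol Section 15.4 (Appendix 4).

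- **Number and design (Methods).** "This PET substudy is planned to recruit up to 14 patients". All have metastatic disease. Each is scanned with [11C]choline and [18F]FLT before lapatinib and again after roughly two weeks of it. The Methods say the sample size calculation is that of the group's previous study with similar tracers.
- **Endpoint (Primary End Point).** The change in uptake of the two tracers "from pre to post treatment with lapatinib".
- **Source data (Statistical considerations).** The SD of FLT Ki "was 2.0 and 3.61 in untreated and metastatic patients and the mean was 3.6 and 7.3 respectively". No choline results are available; they are expected to be similar.
- **Power statement (Statistical considerations).** "A sample size of approximately 14 in each group will have 80% power to detect a difference in means of 3.7". The effect size of 3.7 is explained as "the difference between the metastatic group mean, m1, of 7.3 and the primary group mean, m2, of 3.6". The SDs entered are 3.61 for metastatic and 2 for primary tumours, a ratio of 0.554. The calculation was made "using a Wilcoxon (Mann-Whitney) rank-sum test with a 0.05 two-sided significance level".

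Section 4.2 lists the PET effects on proliferation and MAP kinase activity as a secondary efficacy endpoint for stratum 2.

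**The concern.** The power statement and the design describe different studies. The statement has two independent groups of about 14, one metastatic and one primary, and asks whether their mean Ki differs. The sub-study has one group of at most 14, all metastatic, and asks whether Ki and choline uptake change within a patient on treatment. The rank-sum test used for the sizing assumes independent samples; the endpoint is paired.

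Two inputs fail as a result. The effect size of 3.7 separates two kinds of patient and says nothing about what two weeks of lapatinib might do. The variability needed is the SD of the within-patient change, and the appendix gives only an SD for each patient group.

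A reader of the protocol would take it that the sub-study has 80% power for its primary endpoint, when no power for that endpoint has been worked out. Each participant receives 16.724 mSv from the two sessions by the appendix's own figure, so the number enrolled should rest on the comparison that will be made.

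**Working it through.** **1. Reproduce the stated figure.** Inputs from Appendix 4: means 7.3 and 3.6, SDs 3.61 and 2.0, two-sided alpha 0.05, power 80%, rank-sum test. Noether's formula for two equal groups, with normal data, is

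n per group = (z0.975 + z0.80)² / [6(p − 0.5)²], where p = Φ(difference / √(s1² + s2²)).

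- √(3.61² + 2.0²) = 4.127
- 3.7 / 4.127 = 0.8965, so p = 0.815
- n = (1.960 + 0.842)² / [6 × 0.315²] = 13.2, rounded up to 14 per group, or 28 patients
- by the same formula, power at 14 per group is 82%; simulating the test gives 86% to 87%

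The stated 14 per group is therefore right for the comparison it describes.

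**2. Set it beside the sub-study.**

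| | Power statement | Sub-study |
|---|---|---|
| Groups | metastatic and primary | metastatic only |
| Number | about 14 in each | up to 14 in all |
| Contrast | between patients | within patient, before and after |
| Effect | 3.7, gap between disease stages | not stated |
| Variability | SD in each group | SD of change, not stated |

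For scale, 3.7 would be a fall of 51% from the metastatic mean (3.7 / 7.3).

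**3. What 14 pairs can detect.** For a paired t-test with n = 14 and two-sided 5%, the noncentral t distribution (13 degrees of freedom, noncentrality δ√14, where δ is mean change / SD of change) reaches 80% power at δ = 0.810. For the Wilcoxon signed-rank test with normal differences, simulation gives about 78% power at 0.81 and 80% at about 0.83.

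**4. Put this on the Ki scale.** The SD of change is not in the protocol. Assumption: SD 3.61 at both scans and pre/post correlation rho, so SD of change = 3.61 × √[2(1 − rho)].

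| rho | SD of change | Detectable change at 80% power (0.810 × SD) | As % of 7.3 | Power for a change of 3.7 |
|---|---|---|---|---|
| 0 | 5.11 | 4.14 | 57% | 71% |
| 0.25 | 4.42 | 3.58 | 49% | 82% |
| 0.5 | 3.61 | 2.92 | 40% | 94% |
| 0.8 | 2.28 | 1.85 | 25% | above 99% |

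**5. Two tracers.** If one parameter per tracer is tested at 2.5%, the same paired-t calculation gives 0.91 SD of the paired difference in place of 0.81.

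**The case against.** The strongest reply is that nothing of consequence changes. The sub-study is optional, confined to the UK and limited to 14 patients. The decision rule in Sections 6.2 and 11.2.1 uses tumour response and no PET result. The sizing arithmetic is sound. On the assumptions above, 14 pairs give more than 80% power for 3.7 unless the pre/post correlation is low. This stands as an argument about importance, and it is why the point ranks as should-fix. It does not rescue the claim, because 3.7 was never justified as a lapatinib effect.

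Three stronger readings are tempting, and the protocol does not support them.

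- *The sub-study is underpowered.* A reader might infer this from the mismatch. Without an SD of change or an expected effect it cannot be shown, and pairing may make 14 ample.
- *The data will be analysed with an unpaired test.* The rank-sum test is named only in the power statement. The Results paragraph names no test, and the analysis may be set in the statistical analysis plan.
- *Any one significant parameter will count as success, with a large false-positive rate.* The appendix lists several parameters for two tracers, but speaks of a significant change in parameters without saying that one suffices. The parameters come from the same images and are unlikely to be independent, and multiplicity rules are commonly left to the analysis plan.

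**Conclusion.** Wrong as written, and should be fixed. The 80% power belongs to a comparison that the sub-study does not make; no power is stated for the one it does make. This is a mismatch between sizing and design, not a calculation error.

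The mismatch rests on the text of Appendix 4 alone. Its size depends on an SD of change that the protocol does not give: with SD 3.61 at both scans and correlation from 0 to 0.8, the change detectable with 14 patients runs from 57% down to 25% of the metastatic mean. The choline side is less certain still, since the protocol has no variability data for it. The main trial's response-rate conclusions are unaffected.

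**What to change.** Replace the power paragraph in Appendix 4 with a one-group paired statement:

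- up to 14 patients, with a paired t-test or Wilcoxon signed-rank test on the within-patient change, two-sided 5%;
- 80% power for a mean change of about 0.81 SD of the paired difference (paired t) or about 0.83 SD (signed-rank);
- the detectable Ki change over a range of assumed SDs of change, as in the table above. The team's test-retest data can inform the lower end, but they omit variation between patients in the effect of treatment and so may understate the SD.

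Keep both tracers, because the appendix assigns MAP kinase activity to choline and proliferation to FLT. If each is to carry a formal test, name one parameter per tracer; at 2.5% each the paired-t figure is 0.91 SD. If 14 is really a feasibility number, say so and give the detectable change beside it.

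The cost is wording only, with no extra patients or scans. The drawback is a different stated detectable effect, possibly less favourable than the present text suggests.
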